3 LIST OF ABBREVIATIONS

ABPM:	ambulatory blood pressure monitoring
ACR:	albumin-creatinine ratio
AE:	adverse event
AESI:	adverse event of special interest
ALT:	alanine aminotransferase
ANCOVA:	Analysis of Covariance
AST:	aspartate aminotransferase
BMI:	body mass index
BP:	blood pressure
CEC:	Clinical Endpoint Committee
CI:	confidence interval
CRF:	case report form
CRO:	contract research organization
CSR:	clinical study report
CV:	cardiovascular
DBP:	diastolic blood pressure
DILI:	drug-induced liver injuries
DKA:	diabetic ketoacidosis
DMC:	Data Monitoring Committee
DRF:	Discrepancy Resolution Form
ECG:	electrocardiogram
e-CRF:	electronic case report form
eGFR:	estimated glomerular filtration rate
EMA:	European Medicines Agency
EOSI:	events of special interest
EOT:	End-of-Treatment
FDA:	Food and Drug Administration
FPG:	fasting plasma glucose
FSH:	follicle stimulating hormone
GCP:	Good clinical practice
GCR:	glucose-creatinine ratio
GI:	gastrointestinal
GLP-1:	glucagon-like peptide-1
HbA1c:	hemoglobin A1c
HLGT:	high-level group term
HLT:	high level term
HRT:	hormone replacement therapy
IB:	Investigator's Brochure
ICF:	informed consent form
ICH:	International Council for Harmonisation
IEC:	independent ethics committee

IMP:	Investigational medicinal product
IRB:	institutional review board
IRT:	Interactive Response Technology
ITT:	intent-to-treat
MACE:	major adverse cardiovascular events
MI:	myocardial infarction
MM:	mixed meal
MMTT:	mixed meal tolerance test
NIMP:	noninvestigational medicinal product
OC:	observed cases
PCSA:	potentially clinically significant abnormality
PD:	pharmacodynamic
P-gp:	P-glycoprotein
PI:	Principal Investigator
PK:	pharmacokinetic
PPG:	postprandial glucose
PT:	preferred term
PYY:	peptide YY
SAE:	serious adverse event
SAP:	statistical analysis plan
SBP:	systolic blood pressure
SC:	Steering Committee
SD:	standard deviation
SE:	standard error
SGLT:	sodium-glucose co-transporter
SGLT1:	sodium-glucose cotransporter type 1
SGLT2:	sodium-glucose cotransporter type 2
SMBG:	self-monitoring of blood glucose
SOC:	system organ class
SUSAR:	suspected unexpected serious adverse reaction
T1D:	type 1 diabetes mellitus
T2D:	type 2 diabetes mellitus
TEAE:	treatment-emergent adverse events
TG:	triglycerides
UGE:	urinary glucose excretion
ULN:	upper limit of normal
US:	United States
WOCBP:	women of child-bearing potential

4 INTRODUCTION AND RATIONALE

4.1 BACKGROUND: SOTAGLIFLOZIN AND DISEASE

Sotagliflozin is a dual inhibitor of the sodium-glucose cotransporters type 1 and 2 (SGLT1 and SGLT2) being developed for use in type 2 diabetes mellitus (T2D), a metabolic disorder characterized by hyperglycemia that results from a combination of increased insulin resistance and beta cell dysfunction. The microvascular complications of diabetes are well known and can result in impaired renal function, retinopathy and neuropathy. Other comorbidities that are frequently associated with diabetes are hypertension, obesity, and cardiovascular (CV) disease. Recently, the Centers for Disease Control and Prevention released a report stating that if current trends continue, 1 in 3 Americans will have diabetes by the year 2050. According to the most recent International Diabetes Federation Diabetes Atlas, the estimates in 2015 were that 1 in 11 adults have diabetes, which means 415 million people; estimated to rise to 642 million by 2040 (2).

In 2010, 33 million people in the European Union had diabetes, 9% of the adult population. This number is projected to increase to 38 million by 2030 (3). While these numbers include both people with T2D and type 1 diabetes (T1D), over 90% of adults with diabetes have T2D. Diabetes is among the leading causes of death by disease and is a leading cause of heart disease, stroke, blindness, kidney disease, and amputation (2, 3). Despite the fact that the population of people with diabetes is growing, none of the current therapies is curative and the results of treatment are variable.

Although lifestyle changes, including diet, exercise, and education, are valuable components of diabetes treatment, the vast majority of people with T2D require pharmacological therapy to control the disease. In the United States (US) and Europe, metformin is the standard first-line therapy in the absence of any contraindications or tolerability issues as per guidance from the American Association of Diabetes (4).

Despite the numerous treatment options available, monotherapy fails in many patients as beta-cell function continues to deteriorate leading to progressively increasing hyperglycemia. Aggressive glycemic control with the currently available agents often leads to side effects, most notably weight gain and an increased frequency of hypoglycemia. These concerns emphasize the need to develop new agents that effectively and safely lower glucose in diabetic patients.

In patients with diabetes, it is desirable to maintain blood glucose in the normal range without exhausting the ability of the pancreatic beta-cells to produce insulin. Glucose is transported across the cell membrane by 2 different types of glucose transporters: glucose-facilitated transporters and SGLT proteins (5). In the kidney, after blood is filtered by the glomerulus, glucose passes into the urine, but 99% is reabsorbed, primarily via SGLT2, which is responsible for 90% of glucose reabsorption, while 10% is reabsorbed by SGLT1. When functional SGLT2 is lacking in humans, a significant amount of glucose remains in the urine and is removed from the body (6). This way of reducing blood glucose is not an insulin-dependent mechanism; therefore hyperglycemia may

be reduced while the pancreas is spared from an increased demand for insulin production that is caused by hyperglycemia. Since obesity is a significant comorbidity in T2DM, and insulin resistance is increased in obesity, the caloric loss from glucose in the urine may represent an additional benefit resulting in decreased weight, which should result in decreased insulin resistance (6).

The SGLT1 is expressed predominantly in the gastrointestinal (GI) tract; SGLT1 is responsible for the majority of glucose absorption by the small intestine (7). Inhibition of SGLT1 in the GI tract prevents glucose from being absorbed. Additionally, there is accumulating evidence that SGLT1 inhibition stimulates secretion of glucagon-like peptide-1 (GLP-1) and peptide YY (PYY), gut hormones involved in pancreatic beta-cell function and appetite control, respectively. Reduced glucose absorption in the proximal intestine leads to more glucose being delivered distally, which allows L cells in both the ileum and the colon to sense glucose and its byproducts, and as a result, they secrete GLP-1 and PYY. Although a complete lack of functional SGLT1 may be associated with symptoms of glucose and galactose malabsorption (8), pharmacologic inhibition of SGLT1 by sotagliflozin has not produced these effects in preclinical models or patients with T2D. Selective inhibitors of the SGLT1 transporter are in early stages of development.

Extensive clinical studies conducted for selective SGLT2 inhibitors have established this class as effective agents for the treatment of T2D (9, 10, 11) and have led to approvals by the US Food and Drug Administration (FDA) and the European Medicines Agency (EMA). Studies with sotagliflozin, a potent, dual inhibitor of SGLT2 and SGLT1, have shown that this agent produces significant glucosuria in preclinical animal models, healthy human volunteers, and patients with T2D. Single and multiple-dose administration of sotagliflozin to healthy human patients has resulted in dose-dependent increases in glucosuria. Multiple-dose (28-day) administration in diabetic patients produced improvements in several metabolic parameters, including urinary glucose excretion (UGE), fasting plasma glucose (FPG), hemoglobin A1c (HbA1c), GLP-1, and PYY. These data suggest that sotagliflozin should be of therapeutic benefit to patients with T2D.

4.2 CLINICAL TRIALS OF SOTAGLIFLOZIN IN HUMANS

Approximately 780 subjects (639 assigned to sotagliflozin and 141 assigned to placebo) have participated in completed clinical studies of sotagliflozin. No significant safety concerns have been identified in the sotagliflozin drug program, and sotagliflozin has been well-tolerated in all studies to date. Serious adverse events (SAEs) and discontinuations due to adverse events (AEs) have been infrequent and have been balanced between treatment and comparator groups. Reports of treatment-emergent adverse events (TEAE) across all sotagliflozin studies for which data are available were generally balanced between treatment and comparator groups. The most frequently reported TEAEs ($\geq 2.0\%$) were headache, nausea, diarrhea, constipation, and dizziness, all of which were reported at a frequency greater than placebo. However, most were described as mild to moderate, and most resolved spontaneously.

In completed and ongoing clinical trials, no safety issues in addition to those already described in the current Investigator Brochure were observed. In general, no significant imbalances of SAE/AEs between sotagliflozin and comparators were observed in completed studies.

Cumulatively, during the clinical trial program 8 SAEs were reported by 6 patients (4 T2D and 2 T1D), all of which were assessed as unrelated to study drug; those reported by 4 T2D patients who received sotagliflozin included pulmonary embolism, deep vein thrombosis, bile duct stone, cholangitis and lower limb fracture, while a myocardial infarction (MI) was experienced by a patient receiving placebo. Two SAEs of diabetic ketoacidosis were reported by 2 T1D patients receiving 400 mg once daily sotagliflozin in the Phase 2 T1D study LX4211.1-203-TIDM; both SAEs were assessed as due to failure of insulin delivery via insulin pump.

A drug interaction study with digoxin, a sensitive P-glycoprotein (P-gp) substrate, indicated that sotagliflozin acts as a weak P-gp inhibitor.

More information on the safety of sotagliflozin and on the clinical program can be found in the Investigator Brochure (IB).

4.3 RATIONALE FOR SELECTION OF DOSE

The proposed 400 mg once daily dose is based on the results of the Phase 2b study LX4211.1-202-DM. In this study doses of 75 mg once daily, 200 mg once daily, 200 mg twice daily, and 400 mg once daily sotagliflozin were tested over a 12-week, double-blind period. The 400 mg once daily dose was chosen for further evaluation based on its HbA1c lowering effect and the overall safety and tolerability observed at this dose. At 12 weeks, the 400 mg dose lowered HbA1c by a mean of 0.93%, while placebo lowered HbA1c by a mean of 0.14%. Lower doses were less effective than the 400 mg dose and did not have any advantages in safety or tolerability. The overall incidence of AEs in patients receiving 400 mg once daily was similar to that seen with placebo.

In healthy subjects sotagliflozin was well-tolerated following single doses up to 2000 mg, and in multiple doses up to 800 mg over 10 days. Furthermore, single doses of sotagliflozin (800 mg and 2000 mg) were well-tolerated and did not prolong the QT interval. Additionally, evaluation of metabolites in urine and plasma of healthy subjects resulted in no safety concerns following single doses of 400 mg sotagliflozin. Single doses of 400 mg in combination with sitagliptin, and multiple doses up to 400 mg in combination with metformin over 12 weeks were also well-tolerated in patients with T2D.

4.4 RATIONALE FOR STUDY DESIGN AND CONTROL GROUPS

This study is designed to demonstrate the efficacy and safety of sotagliflozin when used as add-on therapy to metformin in patients with T2D who have inadequate glycemic control. Sotagliflozin plus metformin will be compared to placebo plus metformin. Based on the study design, the protocol stipulates that patients be provided antidiabetic agent rescue therapy according to a predefined algorithm. Safety, tolerability, pharmacokinetic (PK) and pharmacodynamic (PD) effects of sotagliflozin are supported by Phase 1 and Phase 2 studies and toxicology data in rats up to 26 weeks and dogs up to 39 weeks as well as 2-year carcinogenicity data in rats.

To achieve balanced randomization for assessment of the primary endpoint, randomization will be stratified based on preexisting metabolic control (Screening HbA1c \leq 8.0% versus $>$ 8.0%).

Another stratification factor (systolic blood pressure [SBP] <130 mmHg versus \geq 130 mmHg) has been added to ensure balance in randomization for a secondary endpoint (change from Baseline to 12-weeks in SBP for patients with baseline SBP \geq 130 mmHg).

A placebo control will be used to allow for an unbiased assessment of treatment effects and safety data. Bias will be minimized by randomizing the patients to treatment groups, blinding the patients, the Investigators, and the Sponsor to the treatment allocations, and by adjudicating the endpoints in a blinded fashion.

A parallel-group, randomized placebo controlled design was selected because trial participants are exposed to a single treatment and assignment to that treatment is based solely on chance. This design is free of the limitations of competing designs such as crossover in which there may be a carryover of effect from one treatment to the second treatment. Although this carryover effect can be minimized with a washout period, it is possible that some longer term effects may persist. While the sample size of the parallel group design is larger to account for more variability when participants cannot serve as their own control, the above-mentioned limitations of the crossover design have led the randomized controlled trial design to be the standard for therapeutic confirmatory trials for regulatory approval such as this trial.

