10.1.1.1.1 On-site Visit 1 (Week -4) Screening Visit

The following procedures/assessments will be performed at Visit 1 (Week -4):

- IRT to be notified (allocation of ID, registration of screening, collection of demographic information)
- Assessment of all inclusion/exclusion criteria
- Collection of demographic data (age, gender, and ethnic origin)
- Assessment of the patient's medical and surgical history: to include history of T2D, treatment and complications (eye, kidney, amputations, etc); history of smoking/tobacco use; history of alcohol
- Patient diary is dispensed and instructions/training are provided
- Concomitant medication and medication history, including any prior medications for T2D

- Measurement of body height and weight
- Complete physical examination including vital signs (SBP and DBP, temperature, heart rate, and respiratory rate). Three separate seated BPs and heart rate measurements should be taken with at least 1 minute between measurements following a 5-minute rest period, and prior to phlebotomy (see [Appendix E](#) for details of BP procedure)
- 12-lead ECG
- The following laboratory testing (by the central laboratory):
 - Fasting plasma glucose
 - HbA1c
 - Hepatitis serology
 - Serum pregnancy testing for WOCBP
 - serum FSH and estradiol (postmenopausal women only)
 - Hematology
 - Clinical chemistry to include amylase and lipase
 - Fasting lipids
 - Urinalysis (dipstick and microscopy)
- Patients are instructed to return to the site for Visit 2 (Week -2) in a fasted state

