11.4 STATISTICAL METHODS

Continuous data will be summarized by treatment group using the number of observations available, mean, SD, minimum, median, and maximum. Categorical data will be summarized by treatment group using count and percentage.

In general, descriptive statistics of quantitative efficacy and safety parameters (result and change from Baseline) by scheduled visits will be provided on observed cases (OC), ie, inclusion of only patients having non-missing assessments at a specific visit.

The baseline value is defined generally as the last available value before the first dose of double-blind IMP or the last available value prior to randomization for patients who were randomized but never exposed to IMP.

For serum creatinine and eGFR, the Baseline value is defined as the average of all values before the first dose of double-blind IMP for those randomized and exposed or before randomization for those who were randomized but never exposed to IMP.

Analysis of demographics and baseline characteristics, prior and concomitant medications will be provided in detail in the statistical analysis plan (SAP).

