Appendix E Measurement of Blood Pressure and Pulse Rate

The BP measurement device should be calibrated according to manufacturer instructions.

Equipment

1. Blood pressure measurements will be taken by an automated blood pressure monitor or a manual sphygmomanometer
2. Bladder Length – Should nearly or completely encircle the patient’s arm. For many adults, the standard “adult” size bladder is not long enough and the “large” size bladder is recommended
3. Bladder Width – Should be at least 40% of the bladder length.

Patient Factors

Extraneous variables associated with the measurement of BP should be minimized. These include:

1. Food intake, caffeine-containing beverages, cigarette smoking, or strenuous exercise within 2 hours prior to measurement
2. Full urinary bladder
3. The patient should not be allowed to talk while BP is being measured
4. The patient should be placed in the examination room and the cuff should be placed on the patient’s nondominant arm. The proper sized cuff should fit snugly with the lower edge 2 to 3 cm above the antecubital fossa.
5. The patient should be allowed to sit quietly in a comfortably warm place (temperature around 25°C or 77°F) for 5 minutes with the arm supported at heart level, preferably with the cuff in place and with no restrictive clothing on the arm. The patient should be encouraged not to tense his or her muscles.

Nondominant Arm

The patient’s nondominant arm should be the arm declared by the patient as being nondominant. The nondominant arm should then be used for all seated BP measurements throughout the study.

Measurement Technique

[figure not shown]
Following the 5-minute rest period, 3 separate seated BPs should be measured with at least 1 minute between BP measurements and with the cuff fully deflated between measurements.

All 3 BPs will be recorded in the patient’s e-CRF. The mean of the 3 seated BPs will constitute the BP value for that visit.

Three seated pulse rate measurements will be obtained. The mean of the 3 seated pulse rate measurements will constitute the pulse rate value for that visit.

[figure not shown]

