2 STATISTICAL AND ANALYTICAL PROCEDURES

2.1 ANALYSIS ENDPOINTS

2.1.1 Demographic and baseline characteristics

The baseline value (with the exception of serum creatinine and eGFR) is defined as the last available value before the first dose of double-blind investigational medicinal product (IMP) or the last available value prior to randomization for patients who were randomized but never exposed to IMP.

For serum creatinine and eGFR, the baseline value is defined as the average of all values before the first dose of double-blind IMP for those randomized and exposed or before randomization for those who were randomized but never exposed to IMP.

Baseline safety and efficacy parameters are presented along with the summary statistics in the safety and efficacy sections ([Section 2.4.5](#) and [Section 2.4.4](#)).

Demographic characteristics

Demographic characteristics to be summarized are:

- Age (years): Year of informed consent - Year of birth,
- Age categories: (<50, ≥ 50 to <65, ≥ 65 to <75, ≥ 75 years),
- Gender (Male, Female),
- Race (White, Black or African American, Asian, American Indian or Alaska native, Native Hawaiian or other pacific islander, Multiple, Unknown)
- Ethnicity (Hispanic or Latino, Not Hispanic or Latino, Unknown),
- HbA1c (%) at screening visit,
- Randomization strata of HbA1c ($\leq 8\%$, $> 8\%$) at screening visit (data from IRT),
- Mean SBP at screening visit,
- Randomization strata of mean SBP (< 130 mmHg, ≥ 130 mmHg) at screening visit (data from IRT),
- Baseline body mass index (BMI) (kg/m^2) derived as: (Weight in kg)/(Height in meters)²,
- Baseline BMI categories (< 30 , ≥ 30 kg/m^2),
- Country.

Disease characteristics at screening or baseline

Disease history:

- Duration of diabetes (years): (Date of informed consent – Date of diagnosis of diabetes + 1)/365.25,
- Duration of diabetes categories: (<10, \geq 10 years),
- Age at diagnosis of diabetes (years): Year of diagnosis of diabetes – Year of Birth,
- Duration of metformin treatment (years): (date of informed consent - date of first intake of metformin +1)/365.25,
- Daily dose of metformin(mg) at baseline,
- Categorized daily dose of metformin at baseline (<1500, \geq 1500 to <2500, \geq 2500 mg),
- Baseline diabetic microvascular complications (Yes, No) (ie, diabetic retinopathy, diabetic neuropathy, diabetic nephropathy, diabetic peripheral neuropathy (sensory or motor), diabetic autonomic neuropathy, and diabetic foot infection),

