2.4.4.5 Multiplicity issues

To control the family-wise type I error, a fixed-sequence testing procedure will be applied.

Once the primary variable (Change from Baseline to Week 26 in HbA1c) is statistically significant at $\alpha = 0.05$ (2-sided), the following main secondary efficacy variables and ABPM substudy primary endpoint will be tested in the following prioritized order. The testing will stop as soon as an endpoint is found not to be statistically significant at $\alpha=0.05$ (2-sided).

- Change from Baseline to Week 26 in 2-hour PPG following an MM
- Change from Baseline to Week 26 in FPG
- Change from Baseline to Week 26 in body weight
- Change from Baseline to Week 12 in SBP for patients with baseline SBP ≥ 130 mmHg
- Change from Baseline to Week 12 in SBP for all patients
- Change from Baseline to Week 12 in average 24-hour SBP in patients from ABPM substudy (the primary endpoint of the ABPM substudy)
- Proportion of patients with HbA1c $< 7.0\%$ at Week 26.

No multiplicity adjustment will be made on efficacy variables other than those mentioned above.

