For the safety analyses, the baseline for a given parameter is defined as the last available measurement (or the average of all measurements for creatinine and eGFR), including unscheduled assessments, assessed prior to the first administration of double-blind IMP. For the efficacy analyses, the baseline for a given parameter is defined as the last available measurement (or the average of all measurements for creatinine and eGFR), including unscheduled assessments, assessed prior to the first administration of double-blind IMP or the last available value (or the average of all measurements for creatinine and eGFR) before randomization if not treated with double-blind IMP.

Summary statistics by visit for continuous efficacy endpoints

Summary statistics (number, mean, SD, SE, minimum, median, maximum) of continuous efficacy endpoints (observed data and Change from Baseline) will be provided at scheduled visits as per protocol. Summaries showing data by visit will be presented according to the visit number (or re-allocated visit number) and labeled with the targeted approximate day/week.

Last on-treatment value for laboratory variables and vital signs

The last on-treatment value is the final measurement assessed during the treatment epoch, regardless of the introduction of rescue therapy, including measurements at unscheduled visits. Please see details in [Section 2.1.4](#) and [Section 2.4.5](#).

Display of safety data by visit (laboratory variables and vital signs)

Descriptive statistics (number, mean, SD, minimum, median, maximum) of quantitative laboratory variables and vital signs (observed data and change from baseline) during the TEAE period will be provided at scheduled visits. In addition, these summaries will also include a row

for the 'last value on-treatment' to describe the last available on-treatment value (see above). Summaries showing data by visit will be presented according to the visit number (or re-allocated visit number, see [Section 2.5.4](#)) and labeled with the targeted approximate day/week.

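### The Week 12 seated-SBP analyses adjust for one pre-dose visit and leave two earlier visits unused, so a valid comparison is less precise than the collected data allow

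*Protocol*

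**What the plan says.** The fixed sequence in SAP 2.4.4.5 (and Protocol 11.4.2.5) includes "Change from Baseline to Week 12 in SBP for patients with baseline SBP" of 130 mmHg or more, followed by the same change in all patients. Protocol 11.4 sets the baseline: "The baseline value is defined generally as the last available value before the first dose of double-blind IMP". SAP 2.5.4 agrees: "For the efficacy analyses, the baseline for a given parameter is defined as the last available measurement". For seated SBP this is normally Visit 3 (Day 1). Under Protocol Appendix E, "The mean of the 3 seated BPs will constitute the BP value for that visit".

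The same measurement is taken twice before that. At Visit 1 (Protocol 10.1.1.1.1), "Three separate seated BPs and heart rate measurements should be taken with at least 1 minute between measurements"; Visit 2 (10.1.1.2.1) also calls for three assessments.

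Randomization is stratified on Screening SBP, below 130 against 130 mmHg or more. Protocol 4.4 explains that this factor "has been added to ensure balance in randomization for a secondary endpoint", namely the subset endpoint above. Protocol 11.4.2.2 keeps both strata, country and the baseline value in the ANCOVA for every continuous secondary endpoint. SAP 2.4.4.2 removes the SBP stratum for the subset with baseline SBP of at least 130. Both documents report the adjusted mean change in each arm as well as the difference between arms.

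Pooling several pre-dose visits is specified elsewhere: "For serum creatinine and eGFR, the Baseline value is defined as the average of all values before the first dose of double-blind IMP".

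**The concern.** Seated SBP varies from visit to visit, and averaging three readings within one visit does not remove that variation. Two further pre-dose visits carry information about a patient's usual SBP and therefore about the Week 12 value. In the subset model as the SAP writes it, none of that information enters: Visit 3 SBP is the only SBP term. In the all-patient model it enters only as a two-level stratum.

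The stake is precision at two consecutive steps of the sequence. If the subset test fails, the all-patient SBP, ambulatory SBP and HbA1c below 7% tests are not made. Neither document states a power, an SD or an expected size for the subset.

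A second matter is interpretation. Visit 3 SBP both selects the subset and is subtracted to form the change, so the mean change reported within each arm contains regression to the mean.

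**Working it through.** **Nearest figure in the plan.** The only SBP power given is for the ambulatory substudy (Protocol 11.1): 100 per arm, difference 7 mmHg, SD 15, two-sided 0.05. SE = 15 × √(2/100) = 2.12; 7/2.12 = 3.30; power = Φ(3.30 − 1.96) = 0.91, against the stated 90%. It reproduces, but it concerns a different measurement.

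**Assumptions (not in the documents).** 500 patients 1:1 (from the plan); mean usual SBP 130 mmHg; independent visit-to-visit error; between-patient/visit SD of 12/9 (total variance 225, between-visit correlation r = 144/225 = 0.64) or 11/11 (total variance 242, r = 0.50). About half the patients, 250, then have Visit 3 SBP of at least 130.

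**Closed form.** With one pre-dose visit the residual variance is V(1 − r²). With three it is V[1 − 3r²/(1 + 2r)].

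| SDs | one visit | three visits | SE, one visit | SE, three visits |
|---|---|---|---|---|
| 12/9 | 132.8 | 103.7 | 2√(132.8/250) = 1.46 | 2√(103.7/250) = 1.29 |
| 11/11 | 181.5 | 151.3 | 2√(181.5/250) = 1.70 | 2√(151.3/250) = 1.56 |

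The variance ratios are 0.78 and 0.83. This ignores the stratified randomization, which already balances part of the Screening SBP difference, so it slightly overstates the gain.

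**Simulation with the stratified randomization (1,000 trials per scenario).**

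| Analysis | SDs | SE planned | SE with Visit 1-2 mean | (ratio)² |
|---|---|---|---|---|
| Baseline SBP ≥130 | 12/9 | 1.425 | 1.281 | 1.24 |
| Baseline SBP ≥130 | 11/11 | 1.665 | 1.544 | 1.16 |
| All patients | 12/9 | 0.978 | 0.908 | 1.16 |
| All patients | 11/11 | 1.146 | 1.090 | 1.11 |

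Repeat runs moved these by a few hundredths of a mmHg; over all runs the gain was about 15-24% in the subset and 11-19% in all patients.

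**Other assumptions.** With a visit-level SD of 15, r from 0.5 to 0.7 and a mean from 128 to 136, the subset residual variance falls to 0.83 to 0.76 of the planned value. At mean 132 and r = 0.6 the SE goes from 1.45 to 1.29; adding only the binary Screening stratum gives 1.39.

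**Validity of the planned test.** With no drug effect, mean 132 and r = 0.6, 5,000 simulated trials gave a type I error of 0.046 and a mean estimated difference of −0.02 mmHg.

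**Within-arm change with no drug effect.** The cut-off equals the assumed mean, so selected patients lie on average 0.798 SD above it at Visit 3, and a fraction (1 − r) of that excess is lost by Week 12. For 12/9: 15 × 0.798 × 0.36 = 4.3 mmHg. For 11/11: 15.56 × 0.798 × 0.50 = 6.2 mmHg. Both arms show the same fall. It is unchanged by adding a covariate.

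**Effect on power in the subset**, from the closed-form SEs and Φ(difference/SE − 1.96). At 7 mmHg (borrowed from the ambulatory plan) power is already 98-99.8% and rises to above 99%. At an assumed 4 mmHg: 4/1.46 gives 78% and 4/1.29 gives 87%; 4/1.70 gives 65% and 4/1.56 gives 73%.

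**The case against.** The strongest reply is that the planned test is sound. The objective is a comparison with placebo, the last pre-dose value is a conventional baseline, and regression to the mean is the same in both arms in expectation. That stands. A reader might infer from the selection rule that the treatment effect is inflated; the documents do not support this, because Visit 3 SBP precedes the first double-blind dose and the gated quantity is the difference between arms.

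A reader might also infer that the comparison is unprotected because the stratum is cut at Screening and the subset at Baseline. The mismatch is real: under the assumptions tried, 63-82% of the subset comes from the upper Screening stratum. Its consequence is negligible. At mean 132 and r = 0.6 the arms of the subset, about 277 patients, differ by 8 on average (95th percentile 20). A difference of 20 raises the variance by a factor of 1/[1 − (20/277)²], or about 0.5%. Baseline SBP is a covariate in any case.

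Nor does the plan rest on a single reading, since the visit value is a mean of three. It does not wholly ignore Screening SBP either: the stratum is in the all-patient model and in part of the imputation.

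At 7 mmHg the gain hardly moves the power. That also stands; the benefit lies in a smaller effect and a narrower confidence interval. Visits 1 to 3 may not be exchangeable: Protocol 4.5 mentions a white-coat effect, and antihypertensive doses are held constant only from randomization (8.8.1). This could reduce the gain. It cannot bias the comparison, because the covariate is measured before randomization and its slope is estimated.

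Finally, averaging for creatinine and eGFR follows a kidney-disease data standard (SAP 1.5). It shows only that pooling visits is not foreign to this plan.

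**Conclusion.** The point holds as one of efficiency. Both Week 12 seated-SBP comparisons are valid and unbiased as planned, but they leave unused two pre-dose measurements taken by the same method. Using them would be worth roughly 15-24% more patients in the subset and 11-19% in all patients. The direction follows wherever the earlier visits add information beyond Visit 3; the size rests on the assumed variance components and independent visit error.

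Separately, the within-arm mean changes in the subset will include a fall of several mmHg that is not drug effect. This affects how those means are read, not the test. It deserves a caution because Protocol 9.7 motivates the endpoint with a Phase 2 reduction of 10 to 15 mmHg in patients with baseline SBP of at least 130.

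A reader might conclude that the gated subset should be redefined by the Screening stratum. That would remove the within-arm artefact, but it changes the population of a gated endpoint that the protocol consistently defines by baseline SBP, and the tested contrast does not need it.

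**What to change.** 1. Before unblinding, add the mean of the Visit 1 and Visit 2 seated SBP as a second continuous covariate, beside baseline SBP, in both Week 12 SBP ANCOVAs. Keep the endpoint population, the baseline definition and the test order. State what is done if one of the two visits is missing, for example use the other; Screening SBP is needed for stratification, so it should be available.
2. Settle in the same edit whether the Screening SBP stratum stays in the subset model, since Protocol 11.4.2.2 and SAP 2.4.4.2 differ.
3. Add a sentence that within-arm changes in the subset include regression to the mean in both arms and are not estimates of drug effect. The added covariate does not remove this.
4. At most, show the Screening stratum of 130 mmHg or more, with Visit 3 as baseline, as a supportive analysis outside the test sequence.

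The cost is one model term and no new data. Because Protocol 11.4.2.2 also states the ANCOVA terms, the change should be recorded as a departure from the protocol's statistical section. SAP version 3 is still adding analyses and speaks of unblinding as a later step.
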